7.2.4 NTCP modeling

Two NTCP modelling efforts will be conducted for each cognitive outcome domain (attention, memory, executive functioning, working memory, Information/visuomotor processing speed). In the first effort, dose metrics of anatomical structures derived from a brain atlas will be used together with clinical patient factors to develop a prediction model of neurocognitive decline. First, univariable logistic regression analysis will be performed to select clinical parameters associated with cognitive outcome. These variables will be ranked based on their association (area under the curve (AUC) of the univariable logistic regression) with the endpoint. The best ranked variable will be selected first. Subsequently, each next variable will be excluded from the ranking if its Pearson's correlation is r > 0.8 with any previously selected variable. For the remaining variables, we will check whether non-linear transformations (log, square root, inverse transformations, etc.) improves the association. Considered clinical variables in model building are: gender, age at diagnosis, tumour location, treatment modality, pathology, education, time since treatment. The added value of dosimetry to the use of clinical information will be verified in three steps. Initially,

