a multivariable prediction model (logistic regression model with LASSO regularization) will be built with only the clinical variables using a forward stepwise procedure with p = 0.05 (deviance criterion) as critical p-value to stay in the model. Afterwards, the clinical prediction model will be extended by a stepwise addition of dosimetric variables which are ranked in the univariable analysis. In this multivariable prediction model (LASSO), a maximum of 4 variables will be included in each model. Finally, we will test in all models whether proton beam therapy (PBT) itself has an additional independent impact on the outcome risk apart from the already selected dose metrics. If that is the case, this will be investigated further by linear energy transfer (LET) and relative biological effectiveness (RBE) weighted PBT dose maps instead of the standard (RBE=1.1) PBT dose maps. The discriminative ability of the prediction models will be quantified using the AUC and compared between nested models using the likelihood ratio test. To obtain stable prediction models, all modelling steps will be repeated in a 100 times repeated 5-fold cross-validation process. The most frequently obtained models will be selected. Final model coefficients will be determined by fitting these selected models on the complete development dataset. Correction for optimism will be performed using 500 bootstrap samples.

In a second effort, relevant 3D clusters of brain voxels resulting from the brain damage susceptibility heat maps will be included in the modelling. Dose to these brain areas will be used as alternative dosimetric input parameters and the resulting model's performance will be compared to that obtained in the first step. The final NTCP model parameters will be calculated for the whole dataset of patients and per institution in order to detect potential heterogeneity.

Internal validation of the model will be performed using bootstrapping. After external validation, the final NTCP models could possibly be included in decision support software. In case of conflicting neurotoxicity constraints, several 'optimal' solutions to the planning problem (prioritizing one or another brain region) might indeed be possible. This will facilitate plan comparisons and informed decisions on the optimal treatment plan in future patients.

8. Quality assurance

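### Section 7.2.4 gives the NTCP model two conflicting selection rules, a LASSO penalty and forward stepwise selection at p = 0.05, and does not say which governs or whether the final coefficients are penalised

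*Protocol*

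**What the plan says.** All of this is in protocol section 7.2.4, and it applies to each of five cognitive domains.

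- Screening: "First, univariable logistic regression analysis will be performed to select clinical parameters associated with cognitive outcome". Variables are then ranked by univariable AUC, thinned by correlation and checked for transformations. Seven clinical candidates are named: "gender, age at diagnosis, tumour location, treatment modality, pathology, education, time since treatment".
- Clinical model: "logistic regression model with LASSO regularization) will be built with only the clinical variables using a forward stepwise procedure with p = 0.05", where the threshold is described as "deviance criterion) as critical p-value to stay in the model".
- Dose step: "the clinical prediction model will be extended by a stepwise addition of dosimetric variables which are ranked in the univariable analysis". No p-value and no number of dose metrics is given here.
- Size limit, again under the LASSO label: "In this multivariable prediction model (LASSO), a maximum of 4 variables will be included in each model".
- Stability: "all modelling steps will be repeated in a 100 times repeated 5-fold cross-validation process", after which the most frequent models are kept.
- Final fit: "Final model coefficients will be determined by fitting these selected models on the complete development dataset". Whether that fit is penalised is not stated.
- Optimism: a correction with 500 bootstrap samples. Whether it shrinks the coefficients or only corrects the reported performance is not stated.

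**The concern.** In a LASSO the penalty decides which coefficients are non-zero. In forward selection a deviance test decides. Prescribing both for one model leaves the construction rule of the primary objective open, and two analysts following the text could reach different models. The p = 0.05 rule also fails technically on penalised fits, because a deviance difference between two LASSO fits has no standard chi-square reference.

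One reading would reconcile the two: stepwise selection picks the variables and the LASSO only shrinks those that survive. The protocol does not state it. It would also leave the search uncorrected, because a penalty tuned on the survivors does not see the candidates that were discarded.

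The model is meant to give an individual risk for comparing treatment plans. Selection by p-value at this sample size tends to drop real predictors, exaggerate those it keeps and make predicted risks too extreme.

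**Working it through.** **1. The plan's own figure.** Section 7.1 gives 90 and 120 patients for 4 candidate predictors and an rMSPE of 0.1 at event rates φ = 0.2 and 0.5. With rMSPE² ≈ φ(1−φ)(P+1)/N and P = 4:

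- φ = 0.2, N = 90: √(0.16 × 5/90) = 0.094
- φ = 0.5, N = 120: √(0.25 × 5/120) = 0.102

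Simulation gives 0.095-0.097 and 0.090-0.100, so the figure reproduces. It assumes 4 candidates, however. Section 7.2.4 selects up to 4 variables from 7 clinical candidates plus an unstated number of dose metrics, so this calculation does not cover the search.

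**2. Retention and inflation at p = 0.05.** Assume a true predictor with OR 1.5 per SD, so β = ln 1.5 = 0.405. The normal approximation is SE = 1/√(120 φ(1−φ)).

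- φ = 0.2: SE = 1/√19.2 = 0.228, z = 1.78. Retention is P(Z > 1.96 − 1.78) = 43%.
- φ = 0.5: SE = 1/√30 = 0.183, z = 2.22. Retention is P(Z > 1.96 − 2.22) = 60%.

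The mean z given retention is z + pdf(1.96 − z)/retention, where pdf is the standard normal density. At φ = 0.2 this is 1.78 + 0.392/0.427 = 2.70, a factor of 1.5. At φ = 0.5 it is 2.22 + 0.386/0.603 = 2.86, a factor of 1.3.

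**3. Prediction if unpenalised stepwise selection governs.** The simulation used n = 120, 7 clinical and 5 or 20 dose candidates (dose correlation 0.5), and 4 true predictors scaled to a given true AUC. Selection was by deviance at p = 0.05, clinical then dose, with a cap of 4 and 500 data sets per cell (about ±4 points). The AUC, the number and correlation of dose candidates, and p = 0.05 in the dose step are assumptions.

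Percentage of data sets in which the model predicts worse than the average risk (Brier score):

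| Event rate | Dose candidates | AUC 0.50 | 0.60 | 0.65 | 0.70 | 0.75 | 0.80 |
|---|---|---|---|---|---|---|---|
| 0.2 | 5 | 42 | 65 | 61 | 41 | 20 | 5 |
| 0.2 | 20 | 61 | 81 | 81 | 66 | 44 | 20 |
| 0.5 | 5 | 43 | 61 | 41 | 17 | 3 | 1 |
| 0.5 | 20 | 63 | 81 | 71 | 38 | 11 | 4 |

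The median calibration slope is 0.28-0.48 at AUC 0.65 and 0.46-0.68 at 0.75.

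**4. LASSO on the same data**, penalty by 5-fold cross-validation and no cap: 31-38% with no signal, 21-32% at AUC 0.60, 6-17% at 0.65, 1-9% at 0.70 and at most 3% from 0.75. It kept more than 4 variables in 39-62% of data sets at AUC 0.70, so the cap has to be built into the tuning. A separate simulation did cap it at 4. That one used 7 clinical variables, 10-30 dose metrics, a dose OR of 1.7, clinical ORs of 1.4 and 64-80 data sets per scenario. The capped LASSO was worse than the average risk in 0-5% of data sets, and stepwise selection in 35-78%.

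**5. Adding the planned stability and bootstrap steps** (reduced to 4 cross-validation repeats and 30 bootstraps; 100 data sets per cell, about ±10 points). The cells with event rate 0.5, 20 dose candidates and AUC 0.65 or above were not completed.

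| | AUC 0.65 | 0.70 | 0.75 |
|---|---|---|---|
| Most frequent model kept | 30-65% | 15-53% | 4-40% |
| Coefficients also shrunk by the bootstrap slope | 9-28% | 2-19% | 1-8% |

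**The case against.** The strongest reply is that the plan has safeguards. All modelling steps are repeated in cross-validation, and optimism is corrected with 500 bootstraps. Step 5 shows that keeping the most frequent model does not remove the problem, but that shrinking the coefficients by a bootstrap slope from the full procedure removes most of it. This part stands. What is missing is a statement that the bootstrap is used that way, since the final coefficients are said to come from a fit to the complete data.

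A reader might infer that the planned model will usually predict worse than giving every patient the average risk. The documents do not support that. They give neither the expected AUC nor the number of dose metrics, and they attach p = 0.05 only to the clinical step. At AUC 0.75-0.80 with few candidates or a 50% event rate, such a failure is uncommon. With strong effects (dose OR 2.5) at event rate 0.35, stepwise selection followed by LASSO did as well as the capped LASSO, though it did worse at 0.2. LASSO is no guarantee either, as its results at weak signal show.

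It is also fair that the study calls itself exploratory, that use in decision software is only a possibility after external validation, and that tuning details often belong in an SAP. These points lower the severity. They do not resolve two selection rules written into one protocol sentence.

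**Conclusion.** The concern holds as an unresolved conflict in the construction rule of the primary objective, and it should be fixed. The conflict and the missing chi-square reference rest on the text and the method alone. The retention of 43-60% and the inflation of 1.3- to 1.5-fold need only n = 120, the plan's event rates and an assumed OR of 1.5 per SD.

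The harm to prediction is conditional on unpenalised stepwise selection governing. Predicted risks are then too extreme at AUC 0.65-0.75. They are worse than the average risk in 41-81% of data sets at AUC 0.60-0.65 and 17-66% at 0.70, but in only 3-44% at 0.75 and 1-20% at 0.80. Multi-category factors, the transformation search and dropout were not simulated.

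**What to change.** Let the LASSO penalty be the only selection rule in section 7.2.4.

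- Delete the univariable outcome-based selection, the forward stepwise p = 0.05 rule and the stepwise addition of ranked dose variables.
- Per domain, fit one LASSO logistic model on the clinical variables and one on the clinical plus dose variables.
- Choose the penalty by held-out deviance in the planned 100 × 5-fold cross-validation, restricted to at most 4 variables, with a multi-category factor counted as one.
- Keep the penalised coefficients as final.
- Repeat the whole procedure, including any other step that looks at the outcome, inside each of the 500 bootstrap samples.
- Judge the added value of dosimetry by optimism-corrected deviance and AUC, because two separately tuned LASSO models need not be nested.

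The cost is protocol or SAP wording and no new data. The likelihood ratio test between nested models is lost, the cross-validation now tunes the penalty instead of picking the most frequent model, and with strong effects the 4-variable limit makes predictions somewhat too moderate (slope above 1).

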3.1 Trial objectives

The aim of this trial is to study the long-term impact of multimodal treatment (chemotherapy, radiotherapy and surgery) in adult brain and base of skull tumours on neurocognitive functioning using neuropsychological testing combined with advanced MR imaging techniques in a multicenter observational cohort study. We differentiate two main objectives.

The first objective is to build an NTCP model for neurocognitive decline after RT (for each cognitive domain separately), linking dose-volume parameters to structures within the brain susceptible to neurological damage and neurocognitive decline after radiotherapy. These NTCP models will be used to make predictions on neurocognitive decline in future primary brain tumour patients receiving cranial RT. It will provide us with a much needed, evidence-based tool to select the optimal treatment modality for each individual patient and enables us to tailor cranial irradiation towards neurocognition-sparing treatment in the future.

The second objective is to evaluate dose-dependent neurocognitive decline. In particular, we will investigate:

- Prevalence and severity of neurocognitive decline after RT for all cognitive domains
- Brain structures or functional brain connections important in neurocognitive functioning (based on dedicated MRI).
- Dose-dependencies of specific neurocognitive skills after RT in adult brain tumour patients
- Correlations between RT dosimetry and early brain changes (MRI)

With this prospective observational trial, we aim to map the neurocognitive side effects of the irradiation treatment in cranially irradiated patients and the clinical and dosimetrical factors that play a role. Based on these findings, we plan to set up future prospective trials to validate these findings.

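### The NTCP selection in 7.2.4 ignores the direction of the dose effect, so a final model can predict lower risk as dose to a brain structure rises

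*Protocol*

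**What the plan says.** All the relevant rules are in protocol section 7.2.4 unless noted.

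- **Ranking:** "These variables will be ranked based on their association (area under the curve (AUC) of the univariable logistic regression) with the endpoint". This is written where clinical parameters are introduced. The dose sentence, "Afterwards, the clinical prediction model will be extended by a stepwise addition of dosimetric variables which are ranked in the univariable analysis", refers back to the univariable ranking, so the natural reading is that doses are ranked in the same way.
- **Collinearity filter:** "each next variable will be excluded from the ranking if its Pearson's correlation is r > 0.8 with any previously selected variable".
- **Entry or stay:** "using a forward stepwise procedure with p = 0.05 (deviance criterion) as critical p-value to stay in the model", stated for the clinical step. No separate criterion is given for the dose step.
- **Size and penalty:** "In this multivariable prediction model (LASSO), a maximum of 4 variables will be included in each model".
- **Stability:** the steps are repeated in 100 rounds of 5-fold cross-validation, and "The most frequently obtained models will be selected". Coefficients are then refitted on all patients, and optimism is corrected with 500 bootstrap samples.
- **Dose tests in 7.2.3:** two-tailed Wald tests at 0.05.

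On use, section 3.1 says that the tool "enables us to tailor cranial irradiation towards neurocognition-sparing treatment in the future". Section 7.2.4 foresees plan comparison in which "several 'optimal' solutions to the planning problem (prioritizing one or another brain region) might indeed be possible", with possible entry into decision support software after external validation.

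Neither section asks for risk to rise with dose, or for any check on the sign of a dose term.

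**The concern.** In partial-brain radiotherapy a tumour close to one structure is usually far from others, so some structure doses are negatively correlated. If one structure is truly sensitive, a distant structure can look protective merely because it receives little dose when the sensitive one receives much. Chance, and confounding by tumour position, can produce the same picture.

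In a purely descriptive model such a term might be tolerable. In a plan comparison it is not: two plans for the same patient are scored, and the plan that gives more dose to that structure scores better. That runs against the stated purpose of sparing cognition. The term also takes one of only four places in the model.

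**Working it through.** The protocol gives no figure on this point, so there is none to reproduce. Its inputs are n = 120 and event rates 0.2 to 0.5 (section 7.1), and at most 4 variables and five domains (section 7.2.4). The number of dose variables, their correlations and their true effects are assumptions.

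**Step 1. Does any stated step depend on sign?**

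- *AUC of a fitted univariable logistic model.* If A is the AUC of the raw dose, the fitted model takes whichever direction fits, so it reports essentially max(A, 1 - A). A harmful and an equally strong protective slope rank the same.
- *Deviance criterion.* The drop in deviance is approximately (b/SE)², compared with 3.84. It is the same for b and -b. The likelihood ratio comparison of nested models and the two-tailed Wald test behave alike.
- *LASSO.* The penalty is λ·Σ|b|: size, not sign.
- *Filter r > 0.8.* As written it passes every negative correlation, and positive ones up to 0.8.
- *Most frequent model.* This counts recurrence, not plausibility. A pattern driven by tumour position can recur.

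No step depends on direction.

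**Step 2. Hand check of the chance part.** With a two-sided 0.05 criterion, a null dose variable enters with a negative slope with probability 0.025. For 10 independent null candidates:

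- any negative term: 1 - 0.975^10 = 0.22
- any term at all: 1 - 0.95^10 = 0.40

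A simulation of that case (n = 120, 400 runs) gave 0.245-0.253 and 0.417-0.448, in reasonable agreement.

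**Step 3. Hand check of the correlation part.** If dose 1 has slope β per SD and is not in the model, dose 2 takes a slope of about β·ρ. One simulated layout of 24 bilateral structures had negative correlations in 42% of pairs, down to ρ = -0.36. For β = 0.5 or 0.8 the spurious slope is then -0.18 or -0.29. The standard error per SD is about 1/√(n·φ(1 - φ)): 1/√(120 × 0.16) = 0.23 at event rate 0.2, and 1/√(120 × 0.25) = 0.18 at 0.5. The bias is therefore about one standard error, enough to add to chance.

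**Step 4. Simulations.** All use n = 120, AUC ranking, the r > 0.8 filter, deviance entry and a cap of 4, with true dose effects zero or harmful. The table gives the share of models with at least one negative dose coefficient.

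| Set-up | Single pass | Most frequent CV model kept |
|---|---|---|
| 10 dose variables, several correlation patterns, 400 runs per scenario | 4-25% | not run |
| 24 bilateral structures, clinical step first, 500 cohorts per scenario | 11-28% | not run |
| 24 bilateral structures, 300 runs per scenario, 6 repeats of 5-fold | 30-38% | 14-21% |
| 24 bilateral structures, three layouts, 60 cohorts per cell per layout, 10 repeats of 5-fold | 20-29% | 8-17% |
| Assumed geometry, 18 cells of 60 cohorts | 18-38% | 7-25% |

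The resampling step cuts the rate substantially, roughly by half, but does not remove it. The 7-25% spread is largely simulation noise: at the midpoint of 16%, the standard error with 60 cohorts is √(0.16 × 0.84/60) = 0.047, so ±1.96 SE spans about 7% to 25%.

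**Step 5. Which sign is harmful?** Section 7.2.4 allows inverse transformations. If logit p = a + b/D, the slope in D is -b/D², so a positive b means that risk falls with dose. The direction must be judged on the dose-risk slope, not on the raw coefficient.

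**The case against.** - **Unconstrained logistic modelling is legitimate, and a sign rule could be left to an SAP.** True of detail that a protocol does not touch. Here the protocol sets out the ranking, the filter, the penalty, the cap and the choice of the final model; followed as written, they admit the inverse term.
- **Cross-validation is the plan's safeguard.** It is, and rates from a single pass overstate the problem. What is left after it is still not negligible. Bootstrap optimism correction adjusts performance, not direction.
- **Tumour location is a candidate covariate, and the clinical model is built before dose is added.** This is real but partial protection, since location must first survive selection.
- **The sign rule hardly improves prediction.** Correct. In nine scenarios it lowered deviance in new patients by 0.012-0.021 per patient and raised AUC by 0.001-0.005; deviance also fell in all 18 cells of the last simulation. The case rests on how the model is used, not on accuracy. Where no dose matters at all, the rule leaves false harmful terms in place.
- **A wrong sign would be seen before use.** Probably, because final coefficients are fitted explicitly. But dropping a term after seeing it is a data-driven choice, and no external validation criterion on sign is stated. A pattern due to tumour position could validate well on AUC in a similar cohort.

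A reader might infer that planners will be handed such a model. The protocol does not support that: section 2 calls the study exploratory, section 3.1 plans further prospective trials for validation, and section 7.2.4 makes software use only a possibility that follows external validation. A reader might also compound the per-domain rate over five domains as 1 - (1 - p)^5. That assumes independence, but the five models share the same patients and doses, so no such figure should be quoted.

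**Conclusion.** The point holds. As written, the selection in 7.2.4 is blind to the direction of the dose effect, and a final NTCP model may contain a dose term that lowers predicted risk as dose to a brain structure rises. This conclusion needs no simulation.

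Its frequency is uncertain. Roughly 7-25% of models per domain after the most frequent cross-validated model is kept, against 18-38% after a single pass, is an order of magnitude under assumed geometry. None of the runs includes the LASSO. Those with resampling leave out the clinical variables, and two of them used 6 and 10 repeats rather than 100. The p = 0.05 criterion was assumed to apply to dose as well. Other assumed set-ups gave single-pass rates as low as 4%.

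The matter bears on the primary objective and is cheap to settle beforehand, so it should be settled before modelling starts. It is not a fatal flaw, because clinical use is conditional on external validation.

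**What to change.** Add to section 7.2.4, for both modelling efforts:

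1. A dosimetric variable may enter or stay only if the modelled dose-risk slope is non-negative, that is, modelled risk does not fall as dose rises. This is judged on the dose scale after any transformation, including the inverse, in both the univariable and the multivariable fit.
2. The rule is a step of the algorithm within each cross-validation and bootstrap fit and in the final refit. It does not require the same sign in all resamples; unanimity could discard genuine modest effects.
3. Variables excluded by the rule are listed separately as inverse associations, with possible confounding by tumour position named as an explanation.

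The cost is a short addition to the text and a constraint in the modelling code. Apparent fit will be slightly less favourable, and inverse associations move from the model to a side table. The rule does not protect against falsely harmful terms, which still depend on the selection and validation steps.

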4.1 Inclusion criteria

 Adult patients (≥ 18 years at the time of diagnosis) with a primary brain or base of skull tumour, who are amenable for conventionally fractionated radiotherapy (photon or proton irradiation)

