7.1 Sample size

Study subjects will be recruited from the radiation-oncology center of three centers: UZ Leuven, UZ Gent and Iridium Kankernetwerk Antwerpen. From a pragmatic perspective, we estimate to recruit 12-15 patients yearly in each of the three centers, resulting in 120 patients in three years in total.

Cognitive impairment has been reported in primary brain tumour patients and is roughly estimated to be present in about half of patients³⁹⁻⁴⁰. Although limited (good quality) evidence exists for our

type of study, power calculations were performed based on the two most extreme studies (i.e. one showing minimal amount of cognitive impairment⁴¹ and one showing maximal amount of cognitive impairment⁴². In both studies cognitive performance is assessed at baseline and about 12 months after radiotherapy in primary brain tumours. In the study by Moretti et al⁴², we used the cognitive outcome results of patients 9-12 months after radiotherapy (45-60 Gy), since the studied population will receive radiotherapy doses within this range. For power calculations, we used the performance on the digit span forward (processing speed) since the prevalence of impairment on this test was low (<20%). Based on these studies, effect sizes of d= 0,368 and d= 1,271 were found with a power of 0,800 and 0,868 respectively. This power would be 0,979 and 1,000 in our specific explorative study, in case of 120 inclusions. In order to detect this difference after 12 months with a power of 0.800 and a two-sided significance level α =0,05, the total required sample size would thus range between 8-60 patients. Power calculations were performed using Gpower 3.1⁴³.

Sample size calculation for the prediction models was performed using a recently developed software package⁴⁴. Since the event rate of cognitive impairment is unclear, we performed power calculations for the lowest and highest event rate, i.e. 0,2-0,5 (see above). When considering 4 candidate predictors and rMSPE of 0,1, the required sample sizes ranges between 90 and 120 patients respectively. Therefore, including 120 patients will allow building a sufficiently complex prediction model combining four dosimetric and/or clinical features.

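### LET/RBE-weighted proton dose maps are examined only after a positive proton term, a test that at n=120 often misses a moderate modality effect and rarely detects a mis-scaled RBE

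*Protocol*

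**What the plan says.** Section 4.1 admits patients treated with photons or protons, and section 7.2.4 models them in one dataset. The only heterogeneity check named there is by institution.

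Once clinical and dosimetric variables have been selected (at most four per model), section 7.2.4 states that "we will test in all models whether proton beam therapy (PBT) itself has an additional independent impact on the outcome risk", over and above the selected dose metrics. The next sentence sets the consequence: "If that is the case, this will be investigated further by linear energy transfer (LET) and relative biological effectiveness (RBE) weighted PBT dose maps", in place of the standard RBE=1.1 maps. No other route to those maps is given. The section describes no PBT-by-dose term and sets no significance level specific to this test. A critical p-value of 0.05 is stated for the clinical-variable step, and the likelihood ratio test is named for comparing nested models.

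Section 7.1 gives power for the change in cognition at 12 months and a sample size for a four-predictor model. It gives none for the proton term.

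Section 3.1 describes the models as an "evidence-based tool to select the optimal treatment modality for each individual patient".

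**The concern.** The scale on which proton dose is expressed is a direct input to the NTCP model, which is the primary objective. If RBE=1.1 is wrong for the structures concerned, predicted risk under a proton plan is biased, and so is the dose coefficient estimated from the mixed cohort. The protocol foresees the right check but makes it depend on a significance test, so lack of evidence is enough to keep the default. Two features weaken that test.

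- **Power.** The proton group may be a small part of 120 patients, and the endpoint is binary.
- **Aim.** A wrong RBE multiplies dose within proton patients, so the error grows with dose. The PBT term looks for one constant shift in risk between modalities and picks up a scaling error only through its average.

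**Working it through.** **The plan's own figures.** Section 7.1 reports that "effect sizes of d= 0,368 and d= 1,271 were found with a power of 0,800 and 0,868 respectively", a required size of 8-60 patients, and power of 0.979 and 1.000 at 120. A two-sided paired t-test at 0.05 reproduces these: d=0.368 gives power 0.801 at n=60 and 0.979 at n=120; d=1.271 gives 0.867 at n=8 and about 1.000 at n=120. They concern change from baseline and say nothing about the proton term.

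**Inputs for the proton test.**
- From the protocol: N=120; event rate 0.2 to 0.5 (section 7.1).
- Assumed: proton share s of 10-50%; odds ratio 2.5 (log-odds 0.916, about 0.5 SD on the logistic scale); two-sided 0.05; one dose metric in the model.

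**Hand calculation, before dose adjustment.** With event rate p, SE = 1/√(N·s(1−s)·p(1−p)), z = 0.916/SE, and power ≈ Φ(z−1.96).
- Best case, s=0.5, p=0.5: SE = 1/√(120×0.25×0.25) = 0.365; z = 2.51; miss rate 29%.
- Worst case, s=0.1, p=0.2: SE = 1/√(120×0.09×0.16) = 0.761; z = 1.20; miss rate 77%.

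**Simulation with the dose metric in the model.** Logistic outcome, likelihood ratio test of the PBT term, 1,500 trials per cell, dose odds ratio 1.8 per SD, mean proton dose 0.5 SD lower:

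| Proton share | Miss rate, event rate 0.2 | Miss rate, event rate 0.5 |
|---|---|---|
| 10% | 76% | 69% |
| 20% | 63% | 52% |
| 33% | 60% | 41% |
| 50% | 49% | 34% |

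A rerun gave 77, 64, 56 and 54% at event rate 0.2, and 70, 54, 41 and 36% at 0.5. A separate set-up with other dose correlations gave 33-81%. Roughly 35-75% is a fair summary. In the 10% share, event rate 0.2 cell the test rejected about 10% of the time with no effect, so that cell is not an exact 0.05 test.

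**A wrong RBE.** Assume a mean proton dose of 20 Gy to the structure (photon 25 Gy, SD 12) and a dose odds ratio of 1.5 or 2.0 per 10 Gy. If the true RBE is 1.3, the mean proton dose is understated by 20×(1.3/1.1−1) = 3.64 Gy. The average shift in log-odds is 0.364×ln 1.5 = 0.147 to 0.364×ln 2.0 = 0.252, an odds ratio of only 1.16 to 1.29. With the best-case SE of 0.365, z is 0.40 to 0.69 and the miss rate 93% to 89%. Simulation over proton shares of 20-50% gives 88-94%. At a true RBE of 1.5 it gives about 70-90%.

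**Several models.** Five domains are tested. If they were independent and any positive result triggered the check, a per-model miss rate of 52% would become 0.52⁵ = 4%, and 76% would become 0.76⁵ = 25%. Correlation between domains raises these figures, and the trigger may equally be meant model by model.

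**The case against.** A reader might infer that pooling proton with photon patients hinges on this test. It does not: pooling is the default throughout section 7.2.4, and the test decides only whether LET/RBE maps are examined. A reader might also infer that the protocol treats a negative result as proof of equivalence. It draws no conclusion from a negative result; it just leaves RBE=1.1 in place. Nor can a fixed miss rate be called a property of 120 patients, since the proton share and the effect are not in the protocol. And it is not true that a miss is always the likelier outcome: in the table, three of the eight cells fall below one half.

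Further points have weight. The PBT term is tested in all models, so the chance that the check is never triggered can be well below the per-model figure. The study calls itself exploratory, foresees later validation, and mentions decision-support use only after external validation. Treatment modality is undefined: section 2 uses it for surgery, radiotherapy and chemotherapy, and section 7.2.4 lists it as a candidate clinical variable. A margin and interval rule could sit in an SAP that is not shown. A formal equivalence requirement would be hard to meet: with the best-case SE of 0.365 the 95% half-width is 1.96×0.365 = 0.72, a factor of about 2.05 in odds either way.

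These points limit the claim but do not remove it. The conditional rule is fixed in the protocol text. A modality covariate would capture the same constant shift and not a dose-scaling error. External validation is no substitute for checking the dose scale when the model is built.

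**Conclusion.** The concern holds in limited form. Section 7.2.4 lets RBE=1.1 stand unless a PBT term is positive, and that term is a weak and poorly aimed test of the dose scale. Per model, it misses an odds ratio of 2.5 in roughly 35-75% of trials, given the assumed proton share of 10-50%, the protocol's event rates of 0.2-0.5, a two-sided 0.05 level and one dose metric. It misses a true RBE of 1.3 in about 90% under the assumed doses. Loss to follow-up, for which the protocol plans no replacement, would raise these figures; testing across domains lowers the chance that no model triggers the check. The documents do not support a claim that the protocol declares proton and photon dose equivalent, or that the LET/RBE check would necessarily go unrun. The change is worth making because the NTCP model is the primary objective and the check is already foreseen.

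**What to change.** In section 7.2.4, replace the conditional sentence with the following.

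1. Carry out the LET/RBE-weighted analysis of the proton plans as a prespecified sensitivity analysis, whatever the p-value of the PBT term. Report dose coefficients and cross-validated performance under both sets of dose maps.
2. In each domain model, report the PBT and PBT-by-dose estimates with 95% confidence intervals, as diagnostics outside the four-variable cap.
3. State that a non-significant PBT term does not show proton dose at RBE=1.1 and photon dose to be interchangeable.

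No equivalence margin is needed; at this size the intervals would be too wide for one to be useful.

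The cost is a few sentences and the LET/RBE recalculation, which the protocol already foresees conditionally. Radiotherapy plans are uploaded under section 5.1, but the protocol does not say whether LET can be computed from them, so this should be confirmed. The statement on photon-versus-proton use is likely to become more cautious. No extra patients or visits are required.
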